## ABBREVIATIONS

ADL	Activities of Daily Living
AE(s)	adverse event(s)
ATC	Anatomical Therapeutic Chemical
BMI	body mass index
CGI-I	Clinical Global Impression – Improvement
CGI-S	Clinical Global Impression – Severity
CI	confidence interval
COVID-19	Coronavirus disease 2019
CSI	Caregiver Strain Index
C-SSRS	Columbia-Suicide Severity Rating Scale
DMP	Data Management Plan
ECG	electrocardiogram
eCRF	electronic case report form
EOT	End-of-Treatment
ET	Early Termination
GDS	Geriatric Depression Scale
MDS-UPDRS	Movement Disorders Society-Unified Parkinson's Disease Rating Scale
MedDRA	Medical Dictionary for Regulatory Activities
mFSQ	modified Functional Status Questionnaire
MMRM	mixed-effect model repeated measures
MMSE	Mini-Mental State Examination
msec	milliseconds
NPI	Neuropsychiatric Inventory
NPI-Q	Neuropsychiatric Inventory-Questionnaire
PCI	potentially clinically important
PDP	Parkinson's disease psychosis
PGI-I	Patient Global Impression - Improvement
QTcB	QT interval corrected for heart rate using Bazett's formula
QTcF	QT interval corrected for heart rate using Fridericia's formula
SAE(s)	serious adverse event(s)
SAP	statistical analysis plan
SD	standard deviation
SE	standard error
SOC	system organ class

TEAE(s) treatment-emergent adverse event(s)  
VRFCAT Virtual Reality Functional Capacity Assessment Tool

## 1 INTRODUCTION

This statistical analysis plan (SAP) provides a technical and detailed elaboration of the statistical analyses of efficacy and safety data as described in the protocol Amendment 1.0 dated 20 May 2021 and the electronic case report form (eCRF). This SAP will be approved prior to database lock. Specifications for tables, figures, and listings are contained in separate documents (ACP-103-063 Table Shells, ACP-103-063 Figure Shells, and ACP-103-063 Listing Shells, respectively).

## 2 OBJECTIVES AND ENDPOINTS

### 2.1 Primary Objective

The primary objective of this study is to assess the effect of pimavanserin on the activities of daily living (ADLs) in subjects with Parkinson's disease psychosis (PDP) measuring the subject's physical, psychological, social and role functions.

#### 2.1.1 Primary Endpoint

Change from baseline (Week 0) to Week 16 on the modified Functional Status Questionnaire (mFSQ) total score.

### 2.2 Secondary Objectives

- To evaluate the efficacy and benefits of pimavanserin in subjects with PDP on activities of daily living
- To assess the clinician's global impression of severity and improvement of hallucination/delusions

#### 2.2.1 Secondary Endpoints

- Change from baseline to Week 16 on the Schwab and England ADL Scale (Caregiver and Patient Version)
- Change from baseline to Week 16 on the Movement Disorders Society-Unified Parkinson's Disease Rating Scale (MDS-UPDRS) Parts I and II (Caregiver and Patient Version)
- Week 16 Clinical Global Impression – Improvement (CGI-I) score for hallucinations and delusions
- Change from baseline to Week 16 on the Clinical Global Impression – Severity of Illness (CGI-S) score for hallucinations and delusions

- Week 16 Patient Global Impression of Improvement (PGI-I) score for hallucinations and delusions

## **2.3 Exploratory Objectives**

- To assess the extent to which caregivers and families experience additional demands, responsibilities, and difficulties
- To explore the effects of pimavanserin in subjects with PDP on:
  - Functional capacity
  - Cognition
  - Depressive symptoms
  - Nighttime behavior
  - Caregiver burden

### **2.3.1 Exploratory Endpoints**

- Change from baseline to Week 16 on the Virtual Reality Functional Capacity Assessment Tool (VRFCAT) including total time to complete, total number of errors, and total number of forced progressions
- Change from baseline to Week 16 on the Caregiver Strain Index (CSI) total score
- Change from baseline to Week 16 on the Neuropsychiatric Inventory-Questionnaire (NPI-Q) Nighttime Behavior Domain Severity and Caregiver Distress
- Change from baseline to Week 16 on the Geriatric Depression Scale (GDS) (Short Form)
- Change from baseline to Week 16 on the mFSQ score by subscale

## **2.4 Safety Objectives**

- To assess the safety and tolerability of pimavanserin in adults with PDP

### **2.4.1 Safety Endpoints**

The safety and tolerability of pimavanserin will be assessed using the following:

- Treatment-emergent adverse events (TEAEs)
- Columbia-Suicide Severity Rating Scales (C-SSRS) score
- Potentially clinically important (PCI) findings on:
  - Physical examinations

- Clinical laboratory tests
- Vital signs
- Electrocardiogram parameters

### 3 STUDY DESIGN

#### 3.1 General Study Design

This study will be conducted as a 16-week, multi-center, single-arm, open-label study. Pimavanserin (ACP-103) will be administered at a dose of 34 mg to approximately 53 subjects with PDP. Approximately 42 subjects are expected to complete the study, assuming a 20% drop-out rate. Approximately 25 sites in the US will participate in this study.

The duration of participation for individual study subjects will be up to 26 weeks, consisting of the following 3 periods:

[figure not shown]
- Screening period (3-35 days)
- Treatment period (16 weeks)
- Safety follow-up period (30-34 days)

The study will be conducted on an outpatient basis with visits performed at Screening, Baseline (Week 0), Week 2, Week 4, Week 8, Week 12, Week 16 (end of Treatment Period) and Follow-up (at least 30 days and not to exceed 34 days after last dose of study drug). The first dose of study drug (pimavanserin) should be taken on the morning of the day after the Baseline visit.

The study start date is defined as the date the first subject is enrolled, which is the baseline visit date for the first subject. The primary completion date is the last date that subject data was collected for the primary outcome measure. The study completion date is defined as the last date that subject data was collected, which includes the safety follow-up telephone call visit.

[Figure 1](#) illustrates the study design.

**Figure 1 Schematic of Study Design for ACP-103-063**

Abbreviations: EOT: end of trial; ET: early termination; QD: once daily

### **3.2 Schedule of Assessments**

The schedule of events and assessments for the study is presented in the Appendix ([Schedule of Events and Assessments](#)).

### **3.3 Randomization**

This is a single-arm study; therefore, randomization is not applicable.

### **3.4 Blinding**

This is an open-label study; therefore, blinding is not applicable.

### **3.5 Determination of Sample Size**

This is an exploratory study and is not powered for statistical significance. Formal sample size calculations were not used to determine sample size.

### **3.6 Coronavirus Disease 2019**

In March 2020, the emerging coronavirus disease 2019 (COVID-19) pandemic resulted in the implementation of urgent safety measures designed to ensure subject safety ([FDA 2020](#)). Mechanisms to record information on the potential impact of the COVID-19 pandemic on data itself, as well as data collection and integrity, were implemented (as detailed in Appendix B of the Data Management Plan [DMP]). The impact of COVID-19 on the statistical analysis is discussed in each of the relevant sections of this SAP.

Because of possible restrictions due to COVID-19, all references to performing assessments, procedures, and evaluations at the clinic should be understood as including the options of performing these at the subject's home in the presence of a member of the clinical site staff and the subject's caregiver.

## **4 ANALYSIS SETS**

### **4.1 Safety Analysis Set**

The Safety Analysis Set will consist of all subjects who have taken at least 1 dose of study drug. Safety analyses will be based on the Safety Analysis Set.

### **4.2 Full Analysis Set**

The Full Analysis Set will consist of all subjects who receive at least 1 dose of study drug, and have both baseline and at least one post-baseline value for the mFSQ total score. Efficacy analyses will be based on the Full Analysis Set.

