9.4 Subject Populations for Analysis

The **Safety Analysis Set** will consist of all subjects who have taken at least 1 dose of study drug. The Safety Analysis Set will be used for all safety analyses.

The **Full Analysis Set** will consist of all randomized subjects who have taken at least 1 dose of study drug and have both a Baseline value and at least 1 post-Baseline value for the mFSQ total score. The Full Analysis Set will be used for all efficacy analyses.

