9.5.1 Primary Analyses

The primary efficacy endpoint, change from baseline to Week 16 in the mFSQ total score, will be evaluated using a mixed-effects model for repeated measures (MMRM). The response variable is the change from Baseline to Weeks 4, 8, 12, and 16 and the fixed effects include visit (Weeks 4, 8, 12, and 16), corresponding Baseline score, and the Baseline score-by-visit interaction. The mFSQ total score will be calculated as the unweighted mean of the subscale scores (Basic ADL, Intermediate ADL, Psychological Function, Social Activity and Quality of Social Interaction). The Work Performance subscale will be excluded, given the age and non-employment status of the intended patient population.

Summary statistics for the mFSQ total score (observed and change from Baseline), least-squares (LS) means and the corresponding 95% CI will be presented.

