9.5.2 Secondary Analyses

The change from Baseline to Week 16 in the secondary endpoints measured at scheduled visits, including Schwab & England ADL Scale (Patient and Caregiver), MDS-UPDRS Part I (Patient and Caregiver), and MDS-UPDRS Part II (Patient and Caregiver) will be summarized using an MMRM model similar to that described for the primary analysis, except that the Baseline value of the endpoint being analyzed will be included in the model instead of the Baseline mFSQ total score.

For CGI-I the response variable is the observed score at Week 16 and the MMRM will include fixed effects for visit (Week 2, 4, 8, 12, and 16), Baseline CGI-S score, and Baseline CGI-S score-by-visit interaction.

For PGI-I the response variable is the observed score at Week 16 and the MMRM model will include a fixed effect for visit (Week 2, 4, 8, 12, and 16).

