9.5.3 Exploratory Analyses

The change from Baseline to Week 16 in the exploratory endpoints measured at scheduled visits, including individual mFSQ subscales, Caregiver Strain Index total score, NPI-Q Nighttime Behavior domain severity and caregiver distress, Geriatric Depression Scale (Short Form), and the VRFCAT (total time to complete, total number of errors, and total number of forced progressions), will be summarized using an MMRM model similar to that described for the primary analysis, except that 1) the Baseline value of the endpoint being analyzed will be included in the model instead of the Baseline mFSQ total score; and 2) VRFCAT is not

assessed at Weeks 2, 8, and 12, thus the model will only include Weeks 4 and 16. Additional exploratory analyses may be conducted on the VRFCAT data to adjust for deficits of cognition.

In addition to the Week 16 timepoint, each of the primary, secondary, and exploratory endpoints will also be assessed at all other timepoints (Weeks 2, 4, 8, and 12) using the MMRM models described in [Sections 9.5.1, 9.5.2, and 9.5.3](#). These additional timepoints will be considered exploratory.

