5. Gotten along well with other people

The Psychological Function and Quality of Interaction items are scored as follows: 1=all of the time; 2=most of the time; 3=a good bit of the time; 4=some of the time; 5=a little of the time; 6=none of the time.

Work Performance (for those employed during the preceding month) consists of the following items:

1. Done as much as others in similar jobs
2. Worked for short periods of time or taken frequent rests because of your health
3. Worked your regular number of hours
4. Done your job as carefully and accurately as others with similar jobs
5. Worked at your usual job but with some changes because of your health
6. Feared losing your job because of your health

The Work Performance items are scored as follows: 1=all of the time; 2=most of the time; 3=some of the time; 4=none of the time.

The modified FSQ (mFSQ) score will be calculated as the unweighted mean of the following subscale scores: Basic ADL, Intermediate ADL, Psychological Function, Social Activity, and Quality of Social Interaction. The Work performance subscale is excluded due to the age and non-employment status of the intended patient population. Prior to deriving the mFSQ total score, the following items scores are reversed: items 2 and 4 of the Psychological Function, and items 2 and 5 of the Quality of Interaction.

Subscale scores (SS, or transformed scale scores) are calculated according to this formula [[Erratum 1986](#)]:

$$SS = (100/k) \times (\text{Sum of individual item scores} - n)/n$$

Where,

n = number of questions in the subscale for which non-missing, valid information is available

k = maximum minus minimum valid response score

Activities that are not attempted because of non-health-related reasons are scored as 0 and will be excluded from average calculations [[Tedesco et al. 1990](#)]. Therefore, the maximum minus minimum valid response score for the Basic ADL, Intermediate ADL, and Social Activity will have a value of 3.

The mFSQ score will be calculated as (Basic ADL SS + Intermediate ADL SS + Psychological Function SS + Social Activity SS + Quality of Social Interaction SS)/5.

If any of the 5 subscale scores are missing then neither the mFSQ nor the subscale will be imputed.

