## 12 EFFICACY ANALYSES

All efficacy analyses will be performed using the Full Analysis Set. Descriptive summaries of all efficacy endpoints will be provided. No hypothesis testing is planned.

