## 20.2 Schedule of Events and Assessments for ACP-103-063 (continued)

Period	Screening	Treatment						Safety Follow-up
		Baseline		16/EOT				
Visit Week	-5 to 0	0	2	4	8	12	16/EOT	20 a
Visit Number	1	2	3	4	5	6	7/ET b	8
Visit window (days)			±3	±3	±3	±3	±3	+4
Type of Visit	clinic	clinic	clinic	clinic	clinic	clinic	clinic	telephone
MDS-UPDRS Parts I and II (Patient)	X	X	X	X	X	X	X	
MDS-UPDRS Parts I and II (Caregiver)	X	X	X	X	X	X	X	
CGI-S specific to H&D	X	X	X	X	X	X	X	
CGI-I specific to H&D			X	X	X	X	X	
PGI-I specific to H&D			X	X	X	X	X	
VRFCAT	X	X		X			X	
Caregiver Strain Index	X	X	X	X	X	X	X	
Geriatric Depression Scale (Short Form)	X	X	X	X	X	X	X	
Concomitant medication	X	X	X	X	X	X	X	X
Assessment of adverse events		X	X	X	X	X	X	X
Dispense study drug		X	X	X	X	X		
Study drug return			X	X	X	X	X	
Study drug accountability			X	X	X	X	X	

Abbreviations: ADL=activities of daily living; BMI=body mass index; CGI-I=clinical global impression – improvement; CGI-S=clinical global impression – severity; C-SSRS=Columbia-Suicide Severity Rating Scale; ECG=electrocardiogram; EOT=end of trial; ET=early termination; FSQ= functional status questionnaire; H&D=hallucinations and delusions; MMSE=mini-mental state examination; NPI=neuropsychiatric inventory; NPI-Q=neuropsychiatric inventory – questionnaire; PGI-I=patient global impression – improvement; MDS-UPDRS=Movement Disorders Society – Unified Parkinson’s Disease Rating Scale; VRFCAT=virtual reality functional capacity assessment tool

a The safety follow-up telephone call visit is to occur 30 (+4) days after the last dose of study drug, nominally at Week 20 for completers and earlier for ET subjects.

b A subject terminating early should at a minimum complete assessments of safety (vital signs, ECG, AEs, clinical laboratories, C-SSRS) and, if possible, complete all Week 16 assessments.

- c The ECG may be repeated once at Screening in consultation with the Medical Monitor. ECGs can be performed any time before blood sampling or at least 30 minutes after blood sampling during clinic visits.
- d Vital signs (sitting or supine [ $>3$  minutes]) blood pressure, pulse rate, oral temperature, and respiratory rate) will be performed at Screening and each study visit.

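### The Full Analysis Set is defined by the mFSQ but governs every efficacy endpoint, so a subject with no scoreable post-dose mFSQ loses valid data on the other scales

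*SAP*

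**What the plan says.** SAP 4.2 requires at least one dose and that subjects "have both baseline and at least one post-baseline value for the mFSQ total score". Protocol 9.4 sets the same mFSQ condition.

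The scope is general. SAP 12 says "All efficacy analyses will be performed using the Full Analysis Set", and Protocol 9.4 says "The Full Analysis Set will be used for all efficacy analyses". Neither document defines an endpoint-specific set or a sensitivity analysis on a wider set.

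The visit schedules differ by scale:

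- **mFSQ:** Protocol 9.5.1 states "The response variable is the change from Baseline to Weeks 4, 8, 12, and 16". The schedule in SAP 20.2 agrees that there is no FSQ at Week 2.
- **Scales with a Week 2 visit:** Schwab & England, MDS-UPDRS Parts I and II, CGI-S, CGI-I, PGI-I, NPI-Q, Caregiver Strain Index and GDS (SAP 20.2). For CGI-I, Protocol 9.5.2 says the "MMRM will include fixed effects for visit (Week 2, 4, 8, 12, and 16), Baseline CGI-S score".
- **VRFCAT:** Protocol 9.5.3 says it is not "assessed at Weeks 2, 8, and 12, thus the model will only include Weeks 4 and 16".

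At early termination only the safety assessments are a minimum. Beyond those, the subject should, "if possible, complete all Week 16 assessments", and these include the FSQ.

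On scoring, SAP 5.2.4 says "If any of the 5 subscale scores are missing then neither the mFSQ nor the subscale will be imputed". It also leaves out of the average any activity not done for non-health reasons.

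**The concern.** Membership of the analysis set for CGI-I, PGI-I, Schwab & England and the rest depends on a different questionnaire that starts two weeks later. A subject with a Baseline and a Week 2 value on those scales, but no mFSQ after dosing, contributes nothing to any efficacy table.

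This matters for three reasons.

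- SAP 12.4 relies on MMRM being unbiased under missing at random. That argument needs the observed data to be in the model, and here some are removed first.
- SAP 12.8 adds t-tests with last observation carried forward. These would carry such a subject's Week 2 value to Week 16, but the subject is no longer in the set.
- The study has one arm, so no control group offsets selection. If the excluded subjects do worse than the rest, the estimates move toward improvement.

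**Working it through.** **1. The plan's own subject flow.** Protocol 3.1 gives 89 screened, 40% screen failure, 53 enrolled, 20% dropout and 42 completers.

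- 89 × (1 − 0.40) = 53.4, stated as 53.
- 53 × (1 − 0.20) = 42.4, stated as 42.

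The flow reproduces, so about 53 − 42 = 11 dropouts are planned.

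**2. Who can be excluded despite having data on other scales.**

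- *Early leavers.* The subject leaves after Week 2 and before Week 4 without a valid early-termination mFSQ. SAP 4.2 sets no visit condition on the post-baseline mFSQ, so an early-termination FSQ at any time keeps the subject in. A subject who leaves before Week 2 has no scheduled Week 2 values to lose.
- *Unscoreable mFSQ.* If all items of one subscale are excluded (for example, all three Social Activity items coded 0), that subscale has n = 0 and the mFSQ is missing. Baseline is the last non-missing value before the first dose (SAP 5.1), and the FSQ is also done at Screening. The baseline condition therefore fails only if both pre-dose FSQs are unscoreable. The post-baseline condition fails only if every post-baseline FSQ is unscoreable or missing. The documents give no rate for this, so no number is attached.

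**3. How many early leavers.** The documents do not give the timing of dropout. Assume a constant hazard with 20% lost by Week 16:

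- h = −ln(0.8)/16 = 0.01395 per week
- leaving before Week 4: 53 × (1 − exp(−4h)) = 2.9
- leaving between Weeks 2 and 4: 53 × (exp(−2h) − exp(−4h)) = 53 × (0.9725 − 0.9457) = 1.4

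Uniform dropout gives the same: 11 × 2/16 = 1.4. If half of these subjects complete an early-termination FSQ, 0.7 are excluded; if 80% do, 0.3. At the extreme, half of all dropout falls in Weeks 2 to 4 and no early-termination FSQ is done. That gives 11 × 0.5 = 5.5, taken below as 5.

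**4. Effect on a CGI-I mean.** Let m subjects be excluded, with scores d points worse than the rest (d assumed, 0.5 to 1.5). The shift in the Week 2 or LOCF mean is about (m/53) × d.

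| m | d = 0.5 | d = 1.5 |
|---|---|---|
| 1.4 | 0.01 | 0.04 |
| 5 | 0.05 | 0.14 |

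Using 5.5 instead of 5 gives 0.16 at d = 1.5. At d = 0 there is no shift, and a negative d reverses it.

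**5. Effect on the Week 16 MMRM mean.** Week 2 data act on Week 16 only through the within-subject covariance, so the shift is about β × (m/53) × d. With β = 0.5 (assumed), the figures in step 4 halve.

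**6. Scale.** The documents give no SD, so compare in SD units. For 1 to 5 subjects who are 0.5 to 1.0 SD worse:

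- Week 2 or LOCF mean: 1/53 × 0.5 = 0.009 SD to 5/53 × 1.0 = 0.094 SD
- Week 16 MMRM mean with β = 0.5: 0.005 to 0.047 SD
- standard error of a mean at n = 53: 1/√53 = 0.137 SD

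**The case against.** The case for leaving the set alone has several parts.

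- **Rescue by the termination visit.** Protocol 4.4.1 asks sites to make every reasonable effort to complete the termination visit, and the FSQ is part of it. This stands, and it lowers the count. It does not close the gap, because only the safety assessments are a minimum.
- **Not every scale is affected.** A reader might infer that everyone who leaves before Week 4 loses Week 2 data on all other scales. The documents do not support that. VRFCAT has no Week 2 visit, about half of these leavers go before Week 2, and an early-termination FSQ keeps a subject in.
- **Direction.** A reader might also infer that results are tilted toward improvement. Protocol 4.4 lists lack of efficacy and adverse events among the exit reasons, which makes that plausible. It also lists reasons with no evident link to outcome, such as loss of the caregiver or a positive COVID-19 test. Protocol 6.3.5 adds discontinuation after the central read of the Baseline ECG. The direction is an assumption.
- **Transparency.** SAP 6 lists subjects excluded from each set with reasons. That shows the loss but does not restore the data.
- **A common set has a use.** Protocol 1.5 wants to relate benefit on psychosis to functional improvement, which needs both measures in the same subjects. Neither document plans such an analysis, and one could be run on the subjects with both measures.
- **Exploratory study.** No formal power or multiplicity claim is made, which limits the consequences. The secondary estimates will still be reported with confidence intervals.

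**Conclusion.** The point holds. One mFSQ-based set governs all efficacy endpoints, and it discards valid data on eight other instruments for any dosed subject without a qualifying mFSQ. This is at odds with the missing-at-random rationale in SAP 12.4 and with the LOCF tests in SAP 12.8.

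The expected size is small: about 1.4 of 53 subjects, and a CGI-I shift of 0.01 to 0.04 points in the Week 2 or LOCF mean. About 5 subjects and 0.14 points follow only from the extreme assumption, and the Week 16 MMRM shift is smaller in either case. In SD units, every shift computed is below one standard error. These figures rest on assumed dropout timing, an assumed difference d and, for the MMRM, an assumed β. Bias toward improvement is possible if the excluded subjects do worse, but the documents do not establish it. The change is worth making because it is cheap and uses data already collected, not because a large bias is expected.

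**What to change.** Keep the current Full Analysis Set for the mFSQ total and subscale endpoints. For every other efficacy endpoint, use all dosed subjects who have that endpoint's baseline covariate and at least one post-baseline value of that endpoint. For CGI-I the covariate is baseline CGI-S; PGI-I needs none. Report n for each endpoint, and report subjects outside the current set with time and reason of exit.

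The core change is one sentence in SAP 4.2 and Protocol 9.4. The same wording must be aligned wherever the set is cited: the protocol synopsis, Protocol 9.5, and SAP 12 and 12.8. A protocol change goes to the IRB/EC under Protocol 10.7. If only the SAP is changed, SAP 18, which now reports no changes from the protocol, should record it. No new data are needed. The downside is that n will differ between tables.
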